7.1.2 Hypoglycemia

Hypoglycemia is encountered intermittently by patients with T1DM as part of the natural consequence of diabetes management with exogenous insulin administration, and we do not anticipate that this risk will be increased by consuming a low carbohydrate diet.

One study surveyed an online social media group of pediatric T1DM patients who consumed a very low-carbohydrate diet (VLCD) with an average carbohydrate intake goal of 36 grams per day and found low rages of adverse events, including hypoglycemia with seizure or coma (2%), hypoglycemia requiring assistance from others (12%), and hypoglycemia requiring glucagon (4%)¹³. We anticipate that the rates of these events will be considerably lower in the current study given that the carbohydrate intake in both the low-carbohydrate and standard-carbohydrate groups will be substantially higher than in the previously mentioned study.

We will use the following safety provisions to minimize risk of hypoglycemia: Participants will wear a continuous glucose monitor throughout the study period and will be instructed to contact the study team for any episode of hypoglycemia (blood glucose <70). If hypoglycemia occurred, the study team would instruct the patient to be treated orally (administer 15 grams of carbohydrates in liquid form or with glucose tablets) if the patient is responsive and able to consume the treatment orally. If the patient is unresponsive, the study team would instruct the participant's caretaker to administer intramuscular glucagon. The study team will ensure that the participants have an up to date glucagon kit at time of enrollment.

7.1.3 Diabetic Ketoacidosis

During very low carbohydrate intake, the transition to utilizing fatty acids as a fuel source leads to production of ketone bodies in state known as dietary ketosis³⁷. In severely uncontrolled T1DM (ie when exogenous insulin is not adequately supplied), ketone bodies are produced in supranormal quantities and cause ketoacidosis³⁷. In the T1DM population, consuming a low carbohydrate diet could potentially lead to dietary ketosis. However, the low carbohydrate diet that we are utilizing in this study is not intended to induce ketosis. Participants will continue to consume enough carbohydrates at each meal to necessitate insulin administration, which suppresses ketosis.

However, we anticipate that rates of ketoacidosis will be low given low observed rates of DKA in a population of adolescent T1DM patients on a very low carbohydrate diet (about 1%)¹³. Carbohydrate intake was significantly restricted in the very low carbohydrate study to less than half of the amount that we propose in the current study. Therefore, we anticipate that rates of DKA will be equivalent to that typically experienced by patients with T1DM.

To monitor for ketosis, we will measure beta hydroxybutyrate levels at study visits 2 and 3. Participants will additionally be instructed to contact the study team if they have any clinical signs of developing ketoacidosis, including abdominal pain, vomiting, and presence of urine ketones at home.

7.2 Special Protections for Adolescents as Research Subjects Because the study includes adolescent T1DM subjects between ages 1518, special consideration has been given to provisions designed to protect children as outlined in 45 CFR 46, Subpart D.

7.2.1 Justification and rationale for inclusion of adolescent subjects with T1DM

Chronic hyperglycemia worsens both microvascular and macrovascular complications for patients with T1DM^{1,2}. After acute diabetes complications, cardiovascular disease (CVD) is the leading cause of death for adult T1DM patients³, and it is clear that the mechanisms that contribute to macrovascular disease are present early in the natural history of T1DM³⁸. The atherosclerotic changes of macrovascular disease in T1DM appear to begin in childhood and adolescence^{39,40}. Therefore, identifying strategies for the prevention of chronic hyperglycemia to prevent micro- and macrovascular complications is critically important in the childhood and adolescent T1DM population.

Carbohydrate quantity and type affect post-prandial glycemia more than any other dietary factor in non-diabetic populations^{4,5}. Additionally, consuming larger meals is associated with underestimation of carbohydrate quantity and mealtime insulin dose, leading to increased glucose variability⁵. These findings serve as the theoretical basis for implementing a carbohydrate restricted diet to improve HbA1c and decrease glycemic variability with the ultimate goal to prevent CVD.

7.3 Assessment of risk to adolescent participants relative to 45 CFR part 46, subpart D

It is our impression that T1DM subjects would fall under 45 CFR 46.406, as outlined in Vanderbilt's Human Research Protections Program Policy Number IX.A, section II.C. The proposed research is likely to yield generalizable knowledge about these adolescents' condition. Specifically,

- 7.3.1 The risk represents a minor increase over minimal risk.
- 7.3.2 The procedure presents experiences to participants that are reasonably commensurate with those inherent in their actual or expected medical situation.
- 7.3.3 The procedure is likely to yield generalizable knowledge about the participants' disorder or condition, which is of vital importance for the understanding or amelioration of the participants' disorder or condition.

7.3.4 Adequate provisions are made for soliciting assent of the children and permission of their parents or legal guardians as detailed in the present IRB application.

7.4 Discussion of Risks as Part of the Consent Process

The study team will discuss all procedures, risks, and benefits with potential study participants, as part of the consent process. An IRB approved written informed consent document will be required for participation in this study. It is understood that consent is a process and not a discrete event. A participant's decision to withdraw consent will be respected throughout the duration of each subject's participation in this study. It is also understood that there may be as-yet unknown or unanticipated adverse effects of this study. The study team will continually monitor for these effects and consider altering the protocol as needed to ensure patient safety. Changes in the procedures of the study, as well as any change(s) in the risks and/or benefits will be presented to and discussed with the subjects upon approval from the IRB for implementation of such revision(s), and any IRB revised written consent will be signed, as appropriate.

8.0 Reporting of Adverse Events or Unanticipated Problems involving Risk to Participants or Others

8.1 Serious Adverse Events

8.1.1 Defining Serious Adverse Events

Consistent with FDA guidelines, serious adverse events (SAEs) will be defined as any untoward medical occurrence that:

- requires inpatient hospitalization
- results in persistent or significant disability
- is suspected to cause a congenital anomaly or birth defect in a subject's unborn child
- is life-threatening
- results in death
- is considered to be an important medical event based on appropriate medical judgement (e.g. bronchospasms requiring emergency department referral, seizures that might not result in hospitalization).

8.2 Assessing relationship between a SAE and relationship to study procedures

An SAE's relationship to the study procedures will be assessed and graded as either: not related, unlikely, possible, probable, or definite.

8.3 Assessing whether an AE is an anticipated problem

Any AE will be assessed for whether or not it was an anticipated problem. In accordance with Department of Health and Human Services guidance and consistent with 45 CFR part 46, an "unanticipated problem" will

include any incident, experience, or outcome that meets all of the following criteria:

- 1. unexpected (in terms of nature, severity, or frequency) given
 - a. the research procedures that are described in the protocolrelated documents, including the IRB-approved research protocol and informed consent document; and
 - b. the characteristics of the subject population being studied; related or possibly related to participation in the research; and
- 2. suggests that the research places subjects or others at a greater risk of harm.
- 3. related or possibly related to participation in the research;
- 4. suggests that the research places subjects or others at a greater risk of harm than was previously known or recognized.

8.4 Unanticipated, non-serious AEs

All unanticipated, non-serious AEs and the study team's response to the non-serious AE will be included in a report at the time of annual continuing review. The PI will review the AEs and notify the Data Safety Monitor (DSM) and the IRB of any changes needed to the protocol. If needed, appropriate changes will be made to the consent form.

8.5 Unanticipated SAEs

In accordance with IRB policy, any unanticipated SAE that is considered possibly related to participation in the study will be reported within 7 calendar days of the PI's notification of the event to the IRB and DSM. The study team will continue to follow or obtain documentation of the resolution of any SAE.

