ketoacidosis and growth attenuation have been reported in pediatric T1DM patients on a VLCD¹³, therefore, we anticipate low rates of these adverse events with the LCD intervention.

Aim 2 will provide preliminary estimates of the change in the atherogenic lipoprotein profile in patients on a LCD versus SCD. The primary outcome measure will be change in total LDL-P from baseline to 12 weeks after the nutrition intervention. As secondary outcomes, we will measure the change in other contributors to atherogenic lipoprotein load, such as high-density lipoprotein particle (HDL-P) number, small LDL-P number, and LDL size.

Aim 3 will provide preliminary estimates of the change in QOL in patients on a LCD versus SCD. Participants will complete the PedsQL, a validated QOL measure in T1DM patients, and Problem Areas in Diabetes-Teen (PAID-T), a validated measure of diabetes-specific distress, at baseline (week 0) and at 12 weeks after the nutrition intervention^{31,32}. Additionally, parents of participants will complete the WHO-5 Well-Being Index, a questionnaire for assessing subjective psychological well-being³³, and Problem Areas in Diabetes-Parent Revised version (PAID-PR), a validated measure of perceived parental burden associated with caring for a child with diabetes.³⁴

We will perform an independent samples t-test to compare outcomes between groups, in addition to multilinear regression analysis to account for potentially confounding covariates, such as total daily dose of insulin, weight change, glycemic variability as measured by continuous glucose monitoring (CGM), and age.

This proposed research will be the first prospective study to determine the effect of a LCD intervention on key diabetes outcomes in a pediatric T1DM population. This study will also provide a basis of training for a new pediatric investigator in the conduct of clinical trials under the mentorship of a highly successful mentorship team including [name] and [name].

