6.1.3.7 Quality Assurance of Interventions

In order to ensure consistency in the education provided to each group, we will audio record 20% of study visit 2 in each group. Key study personnel who did not perform the educational intervention will review the audio recording and score for fidelity. These audio recordings will be strictly used to ensure consistency of the intervention, will not be used to collect data. Audio files will be contained within REDCap.

6.1.4 Management between study visit 2 and 3

Each T1DM participant's will manage his or her glycemic control before and between study visits using insulin as prescribed by their primary endocrinologist. Participants will be instructed to contact the research team and will be removed from the research protocol in the event of any of the following: weight loss more than 10% from baseline or any episode of DKA or severe hypoglycemia.

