8.6 Adverse Event Reporting

The annual summary of all unanticipated adverse events and any audit reports will be sent to the IRB at the time of continuing review. A copy of this report will also be sent to the NIH who currently funds the PI on a T32 grant.

Data and safety monitoring activities for this study will continue until all subjects have completed their participation and until a sufficient amount of time has passed beyond which any study-related AEs are unlikely.

This protocol will be reviewed annually (at a minimum) by the Vanderbilt IRB. The goal of this process is to determine the risks and benefits of the study in the actual experience of subjects and that measures taken to minimize risks are adequate

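### DKA, severe hypoglycaemia and weight-loss removals that are classed as anticipated have no required report to the safety monitor or IRB, and nothing sets when their frequency in an arm becomes unexpected

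*Combined protocol and SAP*

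**What the plan says.** All references are to the combined protocol and SAP.

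- **Section 8.5 (serious events):** "any unanticipated SAE that is considered possibly related to participation in the study will be reported within 7 calendar days", to the IRB and the DSM. An SAE must therefore be both unanticipated and possibly related before this report is due.
- **Section 8.4 (non-serious events):** "All unanticipated, non-serious AEs and the study team's response to the non-serious AE will be included in a report" at annual continuing review. On the monitor's part in this, "The PI will review the AEs and notify the Data Safety Monitor (DSM) and the IRB of any changes needed to the protocol".
- **Section 8.6 (annual summary):** "The annual summary of all unanticipated adverse events and any audit reports will be sent to the IRB at the time of continuing review", with a copy to the NIH. The DSM is not named as a recipient.
- **Section 8.3 (classification):** every AE is assessed for whether it was anticipated. An event may be unexpected by its nature, its severity or its frequency. It must also be at least possibly related and suggest a greater risk than was already known.
- **Section 6.1.4 (removal):** participants are removed for weight loss above 10% or "any episode of DKA or severe hypoglycemia".
- **Section 7.1 (risks):** suboptimal growth, hypoglycaemia and DKA are listed as considered risks, the last two with rates from a cited survey. Section 2.0 adds that "we anticipate low rates of these adverse events with the LCD intervention".
- **Section 10.2 (analysis):** between-group comparisons cover change in HbA1c, LDL-P and quality of life. No adverse-event summary is described.

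**The concern.** Each stated report depends on an event being unanticipated. The harms that the protocol takes most seriously, judging by its removal rule, are also the ones it lists in advance as known risks. A typical DKA or severe hypoglycaemia can be classed as anticipated and stay with the study team, even if it is an SAE and ends the participant's time in the trial.

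The DSM is the one reviewer outside the study team with a named safety role. As written, the DSM could be unaware of several removals in the low-carbohydrate arm. The protocol's expectation of low event rates under that diet would then have no independent check while the trial runs. Nor does the plan provide for reporting harms by arm at the end, although this pilot is meant to inform a definitive trial.

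**Working it through.** The protocol states no event count, boundary or error rate for safety, so it has no figure of its own to reproduce. The check has two parts: following one event through the rules, and gauging how many events to expect.

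**1. Following one event.** Take one DKA in the low-carbohydrate arm, of ordinary severity, and read the term unanticipated in 8.4 to 8.6 by the definition in 8.3.

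- *Reaching the study team:* yes. Participants are told to contact the team about low glucose (7.1.2) and signs of ketoacidosis (7.1.3). DKA also triggers removal (6.1.4).
- *Classification under 8.3:* the nature of the event is foreseen in 7.1.3. A single case of usual severity need not be unexpected in severity or frequency. The team may reasonably call it anticipated.
- *8.5:* not unanticipated, so no 7-day report is required.
- *8.4 and 8.6:* the same condition keeps it out of the continuing-review report and the annual summary.
- *Removal:* no section requires a removal under 6.1.4 to be reported to the DSM or IRB.
- *10.2:* no harms table by arm.

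A second or third case could be called unexpected in frequency. That judgement needs a running count by arm and a reference to compare it with. Section 7.1 cites survey rates, but no section requires a cumulative count, sets a threshold or schedules a DSM review.

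**2. How many events to expect (illustration only).** Inputs:

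- DKA rate p = 0.01 (about 1%, section 7.1.3). No time base is given, and the source is a survey of a very-low-carbohydrate diet. Treating it as a per-participant risk over the study is an assumption.
- Arm size n = 15 (sections 2.0 and 6.1.1.6) or n = 20 (section 10.1). The sections differ, so both are shown.

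Formulas: P(at least 1) = 1 − (1−p)^n, and P(at least 2) = 1 − (1−p)^n − n·p·(1−p)^(n−1).

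| | n = 15 | n = 20 |
|---|---|---|
| Expected cases, n·p | 0.15 | 0.20 |
| P(at least 1) | 1 − 0.8601 = 14% | 1 − 0.8179 = 18% |
| P(at least 2) | 1 − 0.8601 − 0.1303 = 1.0% | 1 − 0.8179 − 0.1652 = 1.7% |

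One case in an arm is compatible with the cited rate. Two would be unusual enough that a monitor should see them together.

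The result depends on the event and rate used. For hypoglycaemia needing glucagon, cited at 4% (section 7.1.2), P(at least 2) is 12% with 15 per arm and 19% with 20.

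**3. What a small arm can show.** With 0 events in 15, the one-sided 95% upper limit is 1 − 0.05^(1/15) = 18%. This reflects arm size, not the reporting rule, but it shows that an absence of events would give little reassurance. Testing does not help much either. By two-sided Fisher's exact test, 3 versus 0 gives p = 0.22 (15 per arm) or 0.23 (20 per arm), and 5 versus 0 is the smallest such split below 0.05 (0.042 and 0.047). Detection depends on someone reading the cumulative cases by arm.

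**The case against.** The strongest reply is section 8.3. It has every AE assessed and counts unexpected frequency or severity, so an unusual run of DKA, or an unusually severe case, could be classed as unanticipated. If serious and possibly related, it would then go to the IRB and DSM within 7 days. Two cases with a probability near 1% are a fair example of unexpected frequency. In a small single-institution pilot the team would know of both.

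This stands, and it limits the point. A reader might infer that these events have no reporting route at all, that neither of two DKA cases would reach the monitor, or that frequency cannot be judged. The documents support none of these. A conditional route exists, section 7.1 gives reference rates of a kind, and listing a risk in 7.1 does not by itself make every case anticipated.

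What remains is that the route rests on a case-by-case decision by the study team. The definition in 8.3 requires all its criteria together, and its list repeats the relatedness and greater-risk items, which makes it harder to apply.

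Other oversight exists but does not fill the gap:

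- The undertaking in 7.4 to keep monitoring concerns unknown or unanticipated effects.
- The IRB's annual review (8.6) is meant to weigh risks as participants actually experience them, yet the adverse-event summary specified for it omits anticipated events.
- CGM and beta-hydroxybutyrate data are collected, but no section sends them to the DSM.

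Two further reservations are fair. The IRB policy mentioned in 8.5 is not available and may require more, so the gap is shown only for this document. The protocol also does not expect the diet to raise either risk, and it rates the study as a minor increase over minimal risk.

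**Conclusion.** The point holds in a limited form. Followed exactly, sections 8.4 to 8.6 allow a DKA, a severe hypoglycaemia or a weight-loss removal that is classed as anticipated to go unreported to the DSM and IRB. The exception in 8.3 for unexpected frequency or severity is real. Without a by-arm count, a threshold or a scheduled DSM review, however, an excess in one arm could reach the monitor late or not at all.

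The practical size is small in number of events and cannot be stated firmly. The probabilities rest on reading a survey rate with no time base, from a different diet, as a study-period risk. The conclusion rests on the reporting text and does not depend on those figures. This is a cheap improvement to safety oversight; it does not show that participants are unprotected or that an excess is likely.

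**What to change.** 1. **Sections 8.5 and 8.6:** send every SAE, and every removal under 6.1.4 (DKA, severe hypoglycaemia, weight loss above 10%), to the DSM within the same 7 days whether or not it is judged anticipated. Attach a cumulative table by randomised arm each time.
2. **Section 8.6:** include anticipated events in the annual summary.
3. **Section 10.2:** add a descriptive harms table by arm with exact confidence intervals. No significance test is needed.

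The IRB prompt-reporting rules can stay as they are. Separately, the withdrawal list in section 9.0 does not name the three triggers in 6.1.4. The two passages must be reconciled so that it is clear which removals are reportable.

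Cost: protocol wording, a few extra reports in a trial of about 45 people (3 groups of 15), and one table. No new data are collected, because the team already learns of these events.

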8.6 Adverse Event Reporting

The annual summary of all unanticipated adverse events and any audit reports will be sent to the IRB at the time of continuing review. A copy of this report will also be sent to the NIH who currently funds the PI on a T32 grant.

Data and safety monitoring activities for this study will continue until all subjects have completed their participation and until a sufficient amount of time has passed beyond which any study-related AEs are unlikely.

This protocol will be reviewed annually (at a minimum) by the Vanderbilt IRB. The goal of this process is to determine the risks and benefits of the study in the actual experience of subjects and that measures taken to minimize risks are adequate

9.0 Study Withdrawal/Discontinuation

Subjects will be free to withdraw from the study at any time, which will be made clear at enrollment. Subjects will be withdrawn from the study if:

Pregnancy is detected

- The PI's (or designated MD, NP, or PA KSP) medical judgement is that participation places the subject at risk for harm

10.0 Statistical Considerations

10.1 Recruitment and Sample Size Justification

We have targeted an accrual of 40 participants in this pilot study to achieve two goals. First, we require a sufficient number of participants to estimate the effect size and variance of the LCD as a means to reduce HbA1c in T1DM in a future definitive trial. We utilized the method of Whitehead et al. to estimate our pilot study's optimum accrual, which proposes stepped increases in sample size based on the anticipated standard difference, d, between interventions 41,42 . We defined the minimum important difference (MID) in Δ HbA1c between LCD and SCD interventions as 0.3% and estimated a pooled SD of 0.8% based on our literature review9. If d=MID/SDpooled=0.3%/0.8%=0.38, a sample size of 20 participants per arm will optimize future sample size calculations for the definitive study, while allowing for up to 40% dropout. Second, this sample size allows for up to 4 degrees of freedom in multivariable linear regression analysis.

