2.0 Rationale and Specific Aims

We hypothesize that pediatric patients with T1DM who consume a LCD will have improved HbA1c compared with T1DM patients who consume a standard-carbohydrate diet (SCD). We further hypothesize that differences in lipidemia and quality of life (QOL) between the groups will be minimal. To test our hypotheses, we will employ a pragmatic nutrition education intervention. The study will randomize adolescent patients (ages 13-21 years) to one of three groups (n = 15per group). We will instruct participants to consume a LCD (group 1) or a SCD (group 2), or provide no specific recommendations regarding diet (group 3). We will prescribe isocaloric diets for groups 1 and 2 equaling the estimated energy requirements of the Institute of Medicine⁷. Participants on the SCD intervention will consume 45-65% of total daily caloric intake from carbohydrates, 25-35% from fat and 10-30% from protein. Participants on the LCD intervention will consume 25-35% of total daily intake from carbohydrates, 45-65% from fat and 10-30% from protein. Group 3 will serve as a control that receives the same number of education sessions as groups 1 and 2 to teach general diabetes management but without specific dietary recommendations. This study design will allow for discrimination of the effect of the composition of the diet versus the effect of receiving any nutritional prescription.

Nutrition interventions are effective in producing dietary behavior change among adolescents²⁷, particularly when information and communication technologies (ICT) are incorporated²⁸. Previous brief nutrition interventions teaching LCD or low glycemic index diets in T1DM patients have resulted in appropriate dietary adherence^{29,30}. We will provide both traditional and ICT-based education and monitor dietary adherence with a smart-phone based nutritional tracking tool.

Aim 1 will provide preliminary estimates of improvement HbA1c after a nutrition intervention that teaches a LCD versus education reinforcing a SCD to families of pediatric T1DM patients. To determine the primary outcome—change in HbA1c—we will obtain HbA1c at baseline and at 12 weeks after the nutrition intervention. Additionally, we will quantify glycemic variability using continuous glucose monitoring (CGM) as a secondary outcome. Low rates of severe hypoglycemia, diabetic

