6.1.1.6 Randomization

We will then randomize patients to 1 of 3 groups: group 1 is low carbohydrate diet, group 2 is standard carbohydrate diet, group 3 is general diabetes education without dietary recommendation. Each group will contain 15 participants. Random permuted blocks with a fixed size of 3 will be used for randomization into treatment groups.

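### The only sample size justification (40 participants, 20 per arm, up to 40% dropout) fits two arms, but the trial randomises three groups of 15

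*Combined protocol and SAP*

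**What the plan says.** Section 10.1 is the only place that justifies the sample size. It opens with the total: "We have targeted an accrual of 40 participants in this pilot study to achieve two goals". From a minimum important difference of 0.3% in HbA1c change between LCD and SCD and a pooled SD of 0.8%, it derives a standardised difference of 0.38. It then concludes that "a sample size of 20 participants per arm will optimize future sample size calculations for the definitive study", "while allowing for up to 40% dropout". The regression statement rests on the same number: "Second, this sample size allows for up to 4 degrees of freedom in multivariable linear regression analysis".

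The design sections describe a different trial. Section 2.0 randomises adolescents "to one of three groups (n = 15per group". Section 6.1.1.6 says "We will then randomize patients to 1 of 3 groups" and "Each group will contain 15 participants". Sections 5.3 and 6.1.1.6 both use permuted blocks of 3, which suits three groups.

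Section 10.2 plans a t-test between two groups without naming them. The intended pair can be read from section 2.0, where Aim 1 concerns an intervention that "teaches a LCD versus education reinforcing a SCD to families of pediatric T1DM patients".

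**The concern.** Section 10.1 gives the pilot's purpose as estimating the effect size and variance for a later definitive trial. The number per group, the loss that number can absorb and the groups that supply the variance are therefore its main design parameters. The section fixes all of them for a two-arm study, while the trial allocates to three groups of a smaller size.

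The two descriptions cannot both be carried out. Study staff cannot tell whether accrual ends at 40 or 45. A reader planning the definitive trial cannot tell what retention, or what precision for LCD versus SCD, the pilot was designed to give.

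**Working it through.** **Inputs.** From section 10.1: total 40; 20 per arm; dropout up to 40%; minimum important difference 0.3%; SD 0.8%; 4 regression degrees of freedom. From sections 2.0 and 6.1.1.6: 3 groups, 15 per group. Assumed here: a two-sided 95% level, equal loss across groups, and an observed SD equal to the planned 0.8%.

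**The plan's own figures.** 0.3/0.8 = 0.375, stated as 0.38, so this reproduces. 2 x 20 = 40 reproduces. The step from 0.38 to 20 per arm cannot be checked, because the document cites a stepped rule without giving the steps.

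**The three-group design.** 3 x 15 = 45, not 40. The LCD and SCD groups together hold 2 x 15 = 30.

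**Readings that might reconcile the sections.**
- 15 as the completers out of 20: loss is 1 - 15/20 = 25%, not 40%. Sections 2.0 and 6.1.1.6 also give 15 as the size randomised.
- 40 as total accrual over three groups: 40 cannot fill 45 places.
- 20 as the completers: 20/0.6 = 33.3, so 34 per arm would have to be enrolled.
- Section 10.1 as covering only LCD and SCD: that gives 30 under the three-group text, not 40.

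None of these works.

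**Dropout.** At 40% loss, 20 x 0.6 = 12 remain per arm under section 10.1, and 15 x 0.6 = 9 remain per group under the three-group text. Keeping 12 of 15 allows a loss of at most 1 - 12/15 = 20%. The 12 is inferred; the plan states no minimum number of completers.

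**Precision for LCD minus SCD.** Half-width = t(0.975, 2n - 2) x 0.8 x sqrt(2/n), with the two-group degrees of freedom of the section 10.2 t-test.

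| Completers per group | Arises from | df | SE | 95% half-width (percentage points) |
|---|---|---|---|---|
| 20 | 10.1, no loss | 38 | 0.253 | 0.512 |
| 15 | 3 x 15, no loss | 28 | 0.292 | 0.598 |
| 12 | 10.1 at 40% loss, or 3 x 15 at 20% loss | 22 | 0.327 | 0.677 |
| 9 | 3 x 15 at 40% loss | 16 | 0.377 | 0.799 |

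With no loss, 0.598/0.512 = 1.17. At 40% loss, 0.799/0.677 = 1.18.

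**Precision of the SD.** 95% interval = 0.8 x sqrt(df/chi-square quantile), with the 0.975 quantile for the lower limit and the 0.025 quantile for the upper.

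| Source of the SD | No loss | 40% loss |
|---|---|---|
| Two arms of 20 (10.1) | 38 df: 0.654 to 1.031 | 22 df: 0.619 to 1.132 |
| LCD and SCD only, 15 each | 28 df: 0.635 to 1.082 | 16 df: 0.596 to 1.218 |
| All three groups of 15 | 42 df: 0.660 to 1.017 | 24 df: 0.625 to 1.113 |

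**Regression statement.** It is tied to 40 participants, i.e. 40/4 = 10 per degree of freedom. With the LCD and SCD groups only it would be 30/4 = 7.5; with all three groups, 45/4 = 11.25. The plan states no required ratio. The point is only that the sentence describes a sample the three-group design does not produce.

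**The case against.** The strongest reply is that little depends on the mismatch. The arithmetic inside section 10.1 is correct. The aims promise only preliminary estimates. The LCD versus SCD contrast can be read from sections 2.0 and 10.1, so the unnamed pair in 10.2 is not a real puzzle. The half-width moves from 0.51 to 0.60, and there is no precision target for that to breach. If the variance is pooled over three groups, the SD is estimated slightly better than with two arms of 20. The figures for 9 completers apply a 40% loss that the plan never states for groups of 15.

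Most of this stands, and it limits what may be concluded. A reader might infer that 15 per group is too few, or that the pilot fails its purpose. The documents do not support that: whether 15 satisfies the cited rule depends on steps they do not give, and neither size resolves the 0.3% difference. Nor can one say that the variance goal is harmed, since that depends on which groups supply the SD, which the plan leaves open. It is also tempting to say that 15 might mean participants who continue past week 0, but both design sections attach 15 to the act of randomising.

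The reply does not remove the contradiction itself. A pilot still needs one number of arms, one group size and one accrual target.

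**Conclusion.** The point holds as a conflict between sections that has to be corrected. Total accrual is 40 or 45, and the LCD versus SCD comparison holds 40 or 30 participants, depending on which section is followed. The stated allowance of up to 40% dropout belongs to 20 per arm. From groups of 15, the same implied 12 completers survive only if loss is at most 20%. The LCD minus SCD interval is about 17% wider with 15 per group than with 20, and about 18% wider if both lose 40%.

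These sizes illustrate the conflict; they do not show that the trial is too small. They rest on the plan's SD of 0.8%, an assumed 95% level, equal loss across groups and the inferred 12 completers.

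**What to change.** Align sections 2.0, 6.1.1.6, 10.1 and 10.2 on number of arms, size per group, total accrual and dropout allowance. The choice of design is the sponsor's.

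- **Three groups of 15.** Restate section 10.1 as 45 randomised, 15 per group. Replace the per-arm and dropout statement with what this design gives for LCD minus SCD: 15 completers, 0.60; 12 completers (20% dropout), 0.68; 9 completers (40% dropout), 0.80 percentage points. State the SD of 0.8%, the 95% level and the two-group degrees of freedom beside these figures.
- **Three groups of 20.** The total becomes 60, and the group sizes in sections 2.0 and 6.1.1.6 change.
- **Two arms of 20.** Section 10.1 stands, and the three-group text changes wherever it appears, including the block size of 3, which cannot split evenly between two arms.

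If three groups are kept, name the LCD and SCD groups in section 10.2 as the pair compared. Also say whether the SD for the definitive trial comes from those two groups (28 df with 15 each) or from all three (42 df). Under any option, restate the 4 degrees of freedom sentence for the sample actually analysed.

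The cost is rewording and, for 3 x 15, less favourable stated figures. Against the stated accrual of 40, three groups of 15 need 5 more participants and three groups of 20 need 20 more. Two arms of 20 add none, but give up the group 3 control that section 2.0 relies on to separate diet composition from the effect of receiving any nutritional prescription.
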